Primary: Disease control rate at 24 weeks after initiation of tamoxifen (since day 1 cycle 1), defined by absence of radiological progression in conventional imaging

examinations by RECIST 1.1 (Appendix I). Isolated increase of biomarker (chromogranin A) or specific hormone will not be considered progression.

Secondary:

(1) Progression-free survival, defined by time from tamoxifen day 1 cycle 1 to death from any cause or radiological progression by RECIST 1.1, whichever occurs first. Patients alive and without progression at the time of study analysis will be censored for time-to-event analysis.

(2) Biochemical response will be defined by at least 30 percent drop in the marker (chromogranin and / or specific hormone) at any time of treatment in relation to pre-treatment value (s).

(3) Radiological response rate by RECIST criteria 1.1 during the study period.

(4) Disease control rate, defined by absence of radiological progression by RECIST 1.1 criteria, according to the intensity of expression by immunohistochemistry (IHC) of HR and also according to primary site (pancreas, gastrointestinal or lung) during the study period.

(5) Toxicities frequency: Adverse events of grades 2 or more by Common Adverse Event Toxicity Criteria (CTCAE) version 5.0 during the study period.

Exploratory:

(1) Evaluate possible variations in intensity and number of sites between PET-CT gallium-68 pre-treatment and 12 weeks after initiation of tamoxifen as a continuous variable for each capture lesion. Although this examination is part of the evaluation routine of NET, in this study we will evaluate differences in the intensity of uptake with tamoxifen.

(2) Evaluate the percentage of CTC positivity in NET, as well as average number of cells in case of positivity. To evaluate the presence of estrogen and progesterone receptors in CTC.

Methodology:

Study design:

A single-arm, unicentric, single-stage clinical study of tamoxifen for patients with well differentiated neuroendocrine tumors and radiological progression with positive (> 1 percent) HR (estrogen and / or progesterone) expression by IHC.

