Patients eligible for the clinical and radiological criteria and signing the Informed Consent Form (ICF) will have the biopsy material (tumor stored in paraffin) evaluated for IHC of HR. If the expression is positive, eligibility will be complete and patients will receive tamoxifen continuously until radiological progression by RECIST 1.1, unacceptable toxicity or withdrawal of consent. If the expression for HR is negative, the patient will be informed of their ineligibility for this study and will continue to be treated by the Clinical Oncology team without any detriment to their care.

Patients will be followed up by the study team for assessments of:

(1) Safety: first in 3 weeks after tamoxifen day 1 cycle 1, and then every 6 weeks from tamoxifen day 1 cycle 1 for anamnesis with active questioning of disease symptoms and possible adverse events, physical examination and routine laboratory routine (hemogram, biochemistry, liver and renal function);

(2) Efficacy: patients will perform imaging (chest, abdomen and pelvic tomography or abdominal and pelvic resonance imaging) at baseline or pre-treatment and every 12 weeks until progression or intolerance / exit from the study. The image response evaluations will be through RECIST 1.1. For evaluation of the biochemical response, patients will undergo hormonal dosing with serum chromogranin A and specific hormones in cases of functioning NET (eg 5-HIAA dosing in 24-hour urine) at the baseline and every 12 weeks until progression (increased chromogranin and / or the functioning hormone will not be characterized as disease progression if imaging shows progression).

(3) Exploratory assessment: Patients will be assessed for somatostatin receptor expressiveness by the functional examination of PET-CT Gallium-68, which will be performed before treatment and at week 12. This evaluation, because it is exploratory, does not will be part of the definition of disease progression.

Also as an exploratory analysis, a blood sample will be collected to search for circulating tumor cells at the baseline visit (a collection only).

After a period of one year, the consultations laboratory and imaging examinations will be performed every 12 weeks until the disease progresses. Collection and evaluation times are summarized in the Table of Procedures (TABLE 1).

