For immunocytochemistry and for protein expression analysis, the spots of the membranes will be cut and placed in 24-well plates. Each spot will be hydrated with Tris Buffered Saline (TBS) for 10 minutes. Cells will be permeabilized with 0.2 percent Triton X-100 TBS for 5 min at room temperature. After a further TBS wash, the membranes will be incubated for 15 minutes in the dark and at room temperature with a 3 percent solution of hydrogen peroxide, and washed again with TBS. Then the antibodies to be screened will be applied to the spots and incubated for one hour. For the negative control, the primary antibody will be omitted. The development will be done with Dual long HRP system (Dako™) and Diaminobenzidine chromium 3,3 '(DAB) (Dako™). For reading, the spots will be stained with hematoxylin for 1 minute and adhered to the slides with aqueous mount medium. The CTC will be characterized according to the following criteria: nuclear size equal to or greater than 16µm, nuclear contour irregularity, presence of visible cytoplasm, high nucleus-cytoplasm ratio (> 0.8), as described by KREBS et al .19 When any of the criteria described are missing, the cells will be classified as atypical. The results will be given in CTC number per mL of blood.

Methodology for the PET-CT scan with Gallium-68 for the detection of somatostatin receptors

The PET-CT scan with gallium 68 to investigate somatostatin receptors will be performed using the Gemini PET-CT equipment (PET-CT-Dedicated) after administration of 0.1mCi of ⁶⁸Ga-DOTATATE, as already performed in the routine of AC Camargo as a staging method for NET. The images will be started in the minimum interval of 30 minutes and maximum of 60 minutes after the dose. CT - Helicoidal: contiguous anatomical tomographic sections 2.5 mm thick (without intravenous contrast) throughout the body (cranial, thoracic, abdominal, pelvic and lower limb segments). The Standard Uptake Value (SUV) calculation or standard capture value performed for clinically significant areas.

Study population:

Elegibility:

Research participants will be recruited from Clinical Oncology outpatient clinics and must meet all criteria below Inclusion and none of Exclusion:

Inclusion criteria

- Age greater than or equal to 18 years

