Descriptive statistics will be used to report the results of categorical and continuous variables. The time-to-event variables will be reported in medians and Kaplan Meyer curves. The degrees of toxicity will be tabulated. The number of patients discontinuing treatment due to toxicity will be presented.

Efficacy and toxicity analyzes will be performed by intention to treat. Patients receiving at least one dose of tamoxifen will be evaluated for toxicity and efficacy.

Inferential analyzes of the primary outcome according to primary site and IHC HR expression intensity will be conducted to depend on the number of cases per subgroup; if possible, these analyzes will be performed with the chi-square test. The analyzes of intensity of uptake intensity to PET-CT gallium-68 will be with paired T-test. The CTC analysis will be presented in a descriptive way.

Sample Size Calculation

To calculate the sample size, we considered the disease control rate H0 at 6 months of 50 percent (placebo arm result of the phase III studies) 5,23 and H1 as a 6 months disease control rate of 70 percent. A 10 percent bitailed type I error was considered, 80 percent power loss and 30 percent follow up loss. With these calculations, the sample number will be 22 patients.

Recruitment and Study Duration

At the AC Camargo Cancer Center, 30 patients with advanced NET are treated annually. Therefore, considering the patients already under treatment and the possible candidates without previous treatment and that out of every 10 patients, N = 4 will meet eligibility criteria (NETs with positive HR), we estimate to recruit the study population in a maximum period of 3 years and have the first full evaluation in 3 ½ years.

Ethical Considerations

The study will be conducted in accordance with the protocol, Good Clinical Practice guidelines of the International Conference on Harmonization (ICH GCP) and applicable local laws and regulatory requirements. The Free and Informed Consent Term (ICF) must be in accordance with ICH GCP guidelines, local regulatory regulations, and legal requirements. See Appendix 2 for ICF.

The investigator should ensure that each study patient, or his / her legal representative, is fully informed about the nature and objectives of the study and

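### The gallium-68 PET test, read plainly, treats each lesion as an independent pair on the untransformed SUV scale; one mean log ratio per patient would be sounder for this exploratory outcome

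*Combined protocol and SAP*

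**What the plan says.** All references are to the Combined protocol and SAP.

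- **Outcomes, Exploratory (1)** compares the pre-treatment scan with the week-12 scan, covering both how strongly lesions take up tracer and how many sites do so. Uptake is taken "as a continuous variable for each capture lesion", and the stated aim is that "we will evaluate differences in the intensity of uptake with tamoxifen".
- **The PET-CT methodology section** gives the measurement: "The Standard Uptake Value (SUV) calculation or standard capture value performed for clinically significant areas".
- **Statistical plan** gives the test: "The analyzes of intensity of uptake intensity to PET-CT gallium-68 will be with paired T-test".
- **Study design, exploratory assessment**, limits the role of the scan: "This evaluation, because it is exploratory, does not will be part of the definition of disease progression".

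No section names a transformation, a ratio, a percent change or a per-patient summary for uptake. None gives an SUV distribution, a repeatability figure, an expected change, an alpha or a power for this outcome.

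**The concern.** There are two separate problems.

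**Unit of analysis.** A paired t-test with lesions as the pairs assumes that each lesion's change is independent of the others. Lesions in the same patient share the drug exposure, the injection, the uptake time and the scanner session, so their changes will tend to move together. The test then counts more information than the data hold, and its interval is too narrow.

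**Scale.** SUV is a positive ratio measure. If change is proportional, a 15% fall is 0.15 × 10 = 1.5 units in a lesion at SUV 10 and 0.15 × 60 = 9 units in one at SUV 60. The raw differences then have very unequal spread, and a few hot lesions set both the mean and the standard deviation.

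At stake is whether the reported effect of tamoxifen on receptor uptake has an honest error bar and describes the typical patient. The primary outcome is not affected.

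**Working it through.** **The plan's own figure.** The only sample size is for disease control: "With these calculations, the sample number will be 22 patients". Its inputs are a null rate of 50%, an alternative of 70%, 10% two-sided alpha, 80% power (reading the printed phrase as power) and 30% loss. By normal approximation, n = (1.645 × √0.25 + 0.842 × √0.21)² / 0.20² = 36.5, so 37, and 37 / 0.7 = 53 after loss. The figure of 22 therefore does not reproduce. That is a separate, primary-outcome matter which neither supports nor weakens this point. There is no PET figure to reproduce.

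**Inputs for the check.** From the documents: 22 patients, or about 22 × 0.7 = 15 after the planned loss. Assumed: 20 patients with both scans, two-sided 5%, a 15% fall, between-patient SD of log SUV 0.4 to 1.0, SD of the log ratio 0.2 or 0.3, 3 to 5 lesions per patient, and a within-patient correlation of change of 0.3 to 0.5.

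**Step 1: lesions as independent pairs.** With m lesions per patient and correlation ρ, the variance of the mean is understated by a factor D = 1 + (m − 1)ρ. The true false-positive rate is about 2 × [1 − Φ(1.96/√D)].

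| m | ρ | D | False positives at nominal 5% |
|---|---|---|---|
| 3 | 0.3 | 1.6 | 12% |
| 3 | 0.5 | 2.0 | 17% |
| 5 | 0.3 | 2.2 | 19% |
| 5 | 0.5 | 3.0 | 26% |

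This approximation suits the log scale, where simulation gave 12% to 27%. On raw SUV, simulation gave about 11% to 23%. With one value per patient the rate returned to about 4% to 5%.

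**Step 2: raw or log scale, one value per patient, proportional change and error.** On the log scale the effect is ln(0.85) = −0.1625. The noncentrality is 0.1625 × √20 / SD, which is 3.63 for SD 0.2 and 2.42 for SD 0.3. On 19 degrees of freedom, power is 93% and 63%. The raw-scale figures come from simulation (20,000 trials per setting).

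| SD of log ratio | Raw power at between-patient log-SD 0.4 / 0.6 / 0.8 / 1.0 | Log power |
|---|---|---|
| 0.2 | 89 / 83 / 75 / 64% | 93% |
| 0.3 | 57 / 50 / 42 / 34% | 63% |

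The gain runs from 93 − 89 = 4 to 63 − 34 = 29 points. At 22 patients it is 4 to 30, and at 15 it is 6 to 33. Under the null the raw test rejects 3% to 5% of the time, so with one value per patient the scale affects power and not validity.

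**Step 3: change the assumptions.**

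- Additive error (SD 3 SUV units per scan, proportional effect): raw power is 87% to 91%, log power 72% down to 37%. The sign reverses.
- 5% of week-12 values drop to a floor of 0.5 SUV (assumed median SUV 20), one value per patient: at log-ratio SD 0.2, log power is about 58% against 91% to 66% raw; at SD 0.3, 46% against 65% to 40%. The log test mostly loses.
- The same drop-out with 3 to 5 lesions averaged per patient: the log test wins again, by 6 to 8 points.

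**The case against.** The strongest reply is that the plan never says that raw SUV is tested or that lesions are pooled as independent pairs. A lesion-level measurement could still be summarised per patient before testing. That is fair: both readings are the plain default and not a stated rule. The reply shows, however, that scale and unit are left open, and the same amendment settles both.

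Second, the power advantage of the log ratio comes from assuming proportional behaviour, and nothing in the documents establishes it. This stands. A reader might infer a fixed gain, such as 28 points, obtained for nothing. The documents do not support that: they contain no SUV figure, the size and even the sign depend on the assumed error model, and the log ratio brings a different estimand and a floor problem.

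Third, an absolute mean difference does answer the question as the Outcomes section words it. This also stands, and it is why raw differences should still be reported.

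Fourth, a reader might think that the log transform alone repairs the analysis. It does not: lesion-level log ratios still gave 12% to 27% false positives. The repair comes from one value per patient.

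**Conclusion.** The point holds as a low-impact improvement. The firmer part is the unit of analysis: if lesions enter as independent pairs, the nominal 5% test rejects a true null about 11% to 23% of the time, given 3 to 5 lesions per patient and a correlation of 0.3 to 0.5. The numbers are assumed, but the direction follows from any positive correlation.

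The part about scale is conditional. If change and error are roughly proportional to SUV, the log ratio gains about 4 to 29 points of power at 20 patients for a 15% fall, and the mean is no longer set by the hottest lesions. Otherwise the gain may be nil or negative.

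A reader might infer that the trial's efficacy conclusions are at risk. They are not: the scan plays no part in defining progression, and neither the sample size nor any decision rests on it.

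**What to change.** In the Statistical plan, replace the sentence on PET uptake so that it states the following:

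- For each patient, compute the mean of log(SUV week 12 / SUV baseline) over lesions measured on both scans.
- Test these patient means against zero with a one-sample t-test across patients, which is the paired t-test on patient-level log values.
- Report the geometric mean percent change with its confidence interval.
- Report per-patient raw SUV differences as a sensitivity or descriptive analysis.
- Handle lesions that vanish or appear either through the number-of-sites outcome or with a background floor stated before analysis.

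The cost is a few lines of text, with no added patients, scans or data. There are two real downsides. The estimand becomes a relative change. Restricting the ratio to lesions seen on both scans also leaves out those that disappear, so the sites outcome or the floor rule must carry that information, and any floor value will influence the result.

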Even rarer in the literature is the role of antiestrogen therapies as a form of control of this neoplasia. Case reports point to antiproliferative activity of tamoxifen in patients with NET and, in some cases, patients presenting more than 12 months of disease control.¹¹ Reports of control of carcinoid syndrome and even regression of associated retroperitoneal fibrosis have also been described.^{12,13,14} However, the only study to assess the activity of tamoxifen in neuroendocrine tumors dates back to 1984. Sixteen patients were evaluated clinical benefit in only 19 percent of cases and no radiological response. However, in this study, no patient was previously selected for HR tumor expression or degree of differentiation, which we believe limited benefit in disease control.¹⁵

Therefore, based on the premise that there is a need for research and treatment strategies for this rare neoplasm; there is clear therapeutic embezzlement in the SUS due to the high cost of the treatments approved in the country for this neoplasia; NET are tumors that may present positivity to estrogen and / or progesterone receptors; evidence points to the possibility of antiproliferative effect using hormonal therapy, we propose a phase II study of tamoxifen for patients with well differentiated NET and positive for HR, estrogen and / or progesterone expression.

Hypotheses:

Primary: Tamoxifen, an estrogen receptor agonist, exerts antitumor action in patients with well differentiated NET and positive for the expression of HR, estrogen and / or progesterone.

Secondary:

(1) Tamoxifen will promote reduced levels of chromogranin A and / or specific hormones in biochemically active tumors;

(2) The toxicity profile of tamoxifen will be compatible with the toxicity profile described in the literature.

Purposes:

Primary: To evaluate the efficacy of tamoxifen in patients with well-differentiated NETs, with HR, estrogen and / or progesterone expression, and progression.

Secondary: (1) Evaluate progression-free survival; (2) Evaluate biochemical response; (3) objective response rate; (4) disease control rate according to HR expression intensity and primary site; (5) toxicities

Exploratory:

(1) To evaluate variation of intensity and number of sites capturing PET-CT gallium-68 with tamoxifen;

(2) Document the presence of circulating tumor cells (CTC) and possible diagnostic role, such as liquid biopsy.

Outcomes:

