- Histological diagnosis of well differentiated NET (typical and atypical lung carcinoids, NET G1, NET G2 of all gastroenteropancreatic sites and pancreatic NET G3 according to WHO 2017 classification) 20 advanced / metastatic, inoperable, with no possibility of curative treatment
- Immunohistochemical expression ≥ 1 percent for estrogen and / or progesterone receptor
- Disease with radiological progression (at least 10 percent tumor volume growth) in the last 12 months before day 1 cycle 1.
- No possibility of established treatments due to lack of access, risk of toxicities or without clinical indication. Patients who meet criteria for watchful waiting (low-dose disease and non-functioning NET) may be included.

- Measurable disease
- ECOG performance scale 0 to 2.
- Adequate organ function as defined by the following criteria:
 - serum aspartate aminotransferase (AST), serum alanine aminotransferase (ALT) \leq 2.5 times the upper limit of local laboratory normality (LSN-LL);
 - Total serum bilirubin \leq 2.0 x ULN-LL;
 - Absolute neutrophil count \geq 1,500 / mm³;
 - Platelet count \geq 80,000 / mm³;
 - Hemoglobin \geq 9.0 g / dL;
 - Estimated creatinine clearance by the MDRD equation \geq 30ml / min
 - Albumin \geq 3.5 g / dL;
 - INR \leq 1.5
 - Term of free and informed consent signed by the patient or legal representative.

Exclusion criteria

- Patients already on tamoxifen.
- Patients with aggressive disease requiring cytotoxic therapy or locoregional therapies (eg hepatic embolization)
- A history of serious clinical or psychiatric illness that, by clinical judgment, may involve participation risk in this study
- Patients participating in other protocols with experimental drugs.
- Patients with oral food difficulties.
- Patients who underwent major recent surgery less than 4 weeks previously.
- Patients receiving chemotherapy or other oncologic therapy for less than 3 weeks.

- Patients who use oral anticoagulation
- Previous history of deep vein thrombosis or pulmonary embolism in the last 12 months.
- Pregnant or lactating patients.
- Patients with postmenopausal vaginal bleeding with no defined etiology.
- Patients with breast cancer who need to use tamoxifen for this neoplasm
- Another synchronous neoplasm that requires systemic treatment

Treatment:

Tamoxifen:

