Tamoxifen Citrate was the first selective modulator of the developed estrogen receptor. It is a prodrug that has, in itself, little affinity for its target protein, the estrogen receptor. Tamoxifen is metabolised in the liver by the CYP2D6 and CYP3A4 isoforms of cytochrome P450 in its active metabolites afimoxifene and endoxifen, which present 30-100 times more affinity for the estrogen receptor. These active metabolites compete with estrogen for the body binding to the estrogen receptor, possessing 178 percent and 338 percent more affinity for estrogen and alpha receptors, respectively, than estradiol. They have different activities depending on the target tissue. In mammary tissue, they act as receptor antagonists. In other tissues, such as the endometrium, it is agonist. Because of this variable activity, tamoxifen is considered a selective modulator of the estrogen receptor. In hormone receptor-positive breast cancer tumor cells, active metabolites bind to the receptor producing a nuclear complex that decreases DNA synthesis by modulating gene expression, inhibiting estrogenic proliferative effects. The antitumor effect occurs by maintaining the cells in the G0 and G1 phases of the cell cycle, therefore, being a cytostatic rather than cytotoxic agent. Since the demonstration of antineoplastic activity in breast cancer in clinical studies in 1971, tamoxifen has become the prototype drug for

hormone treatment of breast cancer patients positive for hormone receptors at all stages of the disease, both pre- and post- menopause.²¹

The metabolism of tamoxifen is complex (about 10 major metabolites have been identified) and is mediated in the liver by cytochrome P450. Metabolites are excreted mainly by bile. The initial plasma half-life of tamoxifen ranges from 4 to 14 hours, with a secondary half-life of approximately 7 days. The concentration stability of tamoxifen is reached after 4 to 16 weeks of treatment. This prolonged half-life reflects levels of plasma protein binding and enterohepatic recirculation. There is no need for adjustment for renal function and has not been studied in patients with severe hepatic dysfunction.

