- Within 21 days of the first dose of treatment: investigation of the immunohistochemical expression of RH in the paraffin-shaped tumor material. If expression \geq 1 percent, eligibility is confirmed and the following procedures are:

- Within 3 days of day 1 cycle 1: Medical history, including diagnosis and previous treatments, history of other diseases (active and resolved), medications in use and general demographic data. Complete physical examination, ECOG (PS) performance index, body weight and height, and vital signs.
- Laboratory tests: blood count, urea, creatinine, ALT, AST, total bilirubin, sodium, potassium, INR and albumin and pregnancy test for women of childbearing age will be performed within 3 days of the first dose of treatment; these patients will be directed to contraception.
- It will be accepted that baseline imaging has been performed within 8 weeks of the first dose of treatment: Computed tomography (or nuclear magnetic resonance, if applicable) of the abdomen, pelvis and chest.
- All of these above exams are already part of the routine in treating NET at the AC Camargo Cancer Center.

Security Assessment at Week 3:

Adherence and presence of adverse events will be assessed at this time (see Safety Assessment). Will be allowed window of +/- 5 days

Safety evaluation on other weeks:

At each medical appointment, the adverse effects and toxicity related to the treatment will be evaluated by means of anamnesis, physical examination and laboratory evaluation, as follows:

- Complete physical examination, measurement of vital signs, measurement of weight and height, ECOG, use of concomitant medications.
- Evaluation of adherence to treatment.
- Evaluation of adverse events

- Laboratory evaluation: blood count, urea, creatinine, ALT, AST, total bilirubin, sodium, potassium, and others, if clinically indicated.

To grade toxicities, we will use CTCAE 5.0 criteria. Patients who present intolerable grade 2 toxicity or grade 3 that the investigator judges to be related to tamoxifen will have the reduced dose of treatment (see TABLE 3) and will be conducted as previously discussed. All adverse effects will be graded and evaluated whether or not they are related to treatment.

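### The tamoxifen exclusion covers only current use, so a patient whose NET progressed during an earlier tamoxifen course can enter and count in the primary 24-week control rate

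*Combined protocol and SAP*

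**What the plan says.** Three exclusion criteria bear on tamoxifen exposure:

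- "Patients already on tamoxifen", which is current use.
- "Patients with breast cancer who need to use tamoxifen for this neoplasm", which is present need.
- "Patients receiving chemotherapy or other oncologic therapy for less than 3 weeks". The wording is ambiguous. Read as a washout, it removes only very recent users.

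The inclusion criteria require "Disease with radiological progression (at least 10 percent tumor volume growth) in the last 12 months before day 1 cycle 1". They do not say that the growth must have occurred off tamoxifen or since an earlier course ended.

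The baseline assessment collects "Medical history, including diagnosis and previous treatments", and Table 1 also lists prior treatment at baseline. Neither eligibility nor analysis uses the information to identify former tamoxifen users.

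The Study design section describes "A single-arm, unicentric, single-stage clinical study of tamoxifen". The primary outcome is disease control 24 weeks after tamoxifen is started. The Statistical plan evaluates efficacy in all patients who receive at least one dose. The sample size section sets H0 at 50%, from the placebo arms of phase III studies, H1 at 70%, and a sample of 22.

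**The concern.** The trial asks whether starting tamoxifen controls progressing, receptor-positive NET. For a patient whose NET grew during an earlier course, day 1 is a re-challenge with a drug that has already been tried against this tumour. That patient passes every written criterion, and the growth on tamoxifen can itself be the qualifying progression. With one arm, nothing balances such patients, and each one is 1/22 = 4.5 percentage points of the observed rate.

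Former users are conceivable from the document itself. The background states that "Case reports point to antiproliferative activity of tamoxifen in patients with NET", the Tamoxifen section describes the drug's broad use in breast cancer, and the exclusion list foresees breast cancer patients among the candidates. The main risk is that an active treatment looks less active than it is in the patients the trial is about.

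**Working it through.** **Which rule could stop a former user?** Current use: no, the course has ended. Breast cancer that needs tamoxifen: no, unless the need is present. The 3-week therapy rule: only if the course ended very recently, and only on the washout reading. Another synchronous cancer needing systemic treatment: no. The document contains no tamoxifen-naive requirement, no tamoxifen-specific washout, and no stratum or sensitivity analysis for earlier exposure. The gap is in the text and nothing else closes it.

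**The plan's own figure.** With H0 50%, H1 70%, two-sided 10% and 80% power, the usual one-sample formula gives n = ((1.645 × √0.25 + 0.842 × √0.21)/0.20)² = 36.5, so 37 evaluable, and 37/0.70 = 53 after 30% loss. The stated 22 is not reproduced. That is a separate problem. It matters here only because it makes the starting power low; the point below is the change from that start.

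**Effect of former users on a test with n = 22.** The plan gives no decision rule. I assume an exact test with at most 5% in the upper tail, which means success at 16 or more controlled:

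- P(X ≥ 16 | 22, 0.5) = 0.026
- P(X ≥ 16 | 22, 0.7) = 0.494

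Let k patients be former users with control probability q, and the other 22 − k have 70%. The exact tail probabilities at 70% are P(X₂₁ ≥ 15) = 0.5505, P(X₂₁ ≥ 16) = 0.3627, P(X₂₀ ≥ 14) = 0.6080, P(X₂₀ ≥ 15) = 0.4164 and P(X₂₀ ≥ 16) = 0.2375.

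- k = 1: power = q·P(X₂₁ ≥ 15) + (1 − q)·P(X₂₁ ≥ 16)
- k = 2: power = q²·P(X₂₀ ≥ 14) + 2q(1 − q)·P(X₂₀ ≥ 15) + (1 − q)²·P(X₂₀ ≥ 16)

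With q = 0.5, the plan's reference rate:

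- k = 1: 0.5 × 0.5505 + 0.5 × 0.3627 = 0.457
- k = 2: 0.25 × 0.6080 + 0.50 × 0.4164 + 0.25 × 0.2375 = 0.420

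With q = 0.3, a more pessimistic assumption that has no source in the documents:

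- k = 1: 0.3 × 0.5505 + 0.7 × 0.3627 = 0.419
- k = 2: 0.09 × 0.6080 + 0.42 × 0.4164 + 0.49 × 0.2375 = 0.346

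| Former users who progressed on tamoxifen | Power, q = 0.5 | Power, q = 0.3 |
|---|---|---|
| 0 | 49% | 49% |
| 1 | 46% | 42% |
| 2 | 42% | 35% |

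**The other direction.** Take former users who did well before, with an assumed 90% control rate, and a 50% rate in everyone else. At 50%, P(X₂₁ ≥ 15) = 0.0392, P(X₂₁ ≥ 16) = 0.0133, P(X₂₀ ≥ 14) = 0.0577, P(X₂₀ ≥ 15) = 0.0207 and P(X₂₀ ≥ 16) = 0.0059.

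- One such patient: 0.9 × 0.0392 + 0.1 × 0.0133 = 0.037
- Two: 0.81 × 0.0577 + 0.18 × 0.0207 + 0.01 × 0.0059 = 0.050

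The chance of a false success rises from 2.6% to 3.7% or 5.0%. Even the larger figure is about the nominal 5% upper tail of a two-sided 10% test.

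**The case against.** The strongest objection is that these patients may not exist. The document gives no count of past tamoxifen users and presents the drug's use in NET as rare: case reports and one 16-patient study from 1984. This stands. Zero is compatible with everything written, and one or two of 22 is only an assumption.

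A reader might also infer more than the documents support, in four ways.

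- **That a past failure is certain to fail again.** Setting q = 0 gives power of 36% with one such patient and 24% with two. Nothing supports 0%. Stable disease counts as control, the plan's own placebo reference is 50%, and every participant must show recent progression, so that entry requirement does not set former users apart.
- **That past responders bias the result upward just as easily.** They must be off tamoxifen and still show at least 10% growth within 12 months before day 1. This is possible if the growth came before the earlier course or after it stopped, but it is a barrier. Growth on tamoxifen meets the criterion directly.
- **That baseline measurements would be contaminated by residual drug.** The protocol describes tamoxifen "with a secondary half-life of approximately 7 days", so 0.5³ = 12.5% would remain after three weeks. The argument needs the ambiguous therapy rule read as a washout, and a patient who stopped just then. Nothing in the documents shows that this residue changes scans or markers, and the PET comparison is exploratory.
- **That any past tamoxifen user brings a known answer.** Someone who finished a breast cancer course before the NET arose has shown nothing about NET response.

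It is also fair to say that the plan handles part of this. Current users and those who need the drug are out, and earlier treatments are recorded. Recording alone, however, neither removes former users nor commits the analysis to showing their effect.

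**Conclusion.** The point holds as a gap in the scope of a stated exclusion: tamoxifen taken and stopped earlier is not covered, and a patient whose NET grew on it can qualify through that growth and count in the primary result. The size is modest and conditional. Power at 70% loses about 4 or 7 percentage points with one or two such patients at the 50% reference rate (49% to 46% or 42%), and about 8 or 15 points at 30% (to 42% or 35%). With no such patients the loss is zero. These figures rest on an assumed number of former users, assumed control rates and an assumed success rule of 16/22. The documents do not support reading this as a large or symmetric bias. It is worth correcting because the correction is cheap and a 22-patient test has little room for patients who do not address its question.

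**What to change.** Extend the exclusion to previous tamoxifen taken while the NET was present. A simpler version to apply is any previous tamoxifen, which reaches somewhat further than the problem because it also removes people whose course ended before the NET arose. Barring every past anti-oestrogen would go further than the defect requires. Check the criterion against the prior-treatment history already collected, before the first dose.

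If the sponsor prefers to keep former users, state in the Statistical plan that the primary 24-week control rate will be reported with and without them, and record whether the NET was present and progressed during the earlier course.

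The cost is one amended line, no new procedure, and the loss of probably few candidates. No input to the sample size calculation changes.
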